7.2. Permanent Discontinuation of Study Drug

There are two types of permanent discontinuation of study drug:

- Temporary study drug interruption that becomes a permanent discontinuation:
 - After a temporary study drug interruption, if a safety concern for the patient has not stabilized or resolved or if the investigator suspects that study drug may be responsible, the investigator may consider the temporary interruption to be a permanent discontinuation.

- The investigator should make best efforts to contact the Medical Monitor before considering any temporary interruption as a permanent discontinuation.
- Permanent study drug discontinuation that is not preceded by a temporary study drug interruption
 - The investigator should make best efforts to contact the Medical Monitor before considering any permanent study drug discontinuation.

In all cases, patients should be encouraged to discuss stopping study drug with the investigator or the investigator's designee. See [Section 6.5](#) regarding potential dose reduction of study drug. Best efforts should be made to address the patient's questions, adjust concomitant medical therapies if needed and arrange follow-up safety assessments. Refer to [Section 7.2.1](#) for management of patients that permanently discontinue study drug.

Any permanent discontinuation of study drug should be recorded in the CRF including the reason for permanent discontinuation, if a patient is willing to provide it. If the patient is unwilling to provide the reason, that too should be documented.

Reasons for permanent study drug discontinuation may include any of the following:

- Patient request
- Adverse event
- Pregnancy
- Criteria for possible renal toxicity are met ([Section 7.3](#))
- Criteria for possible hepatotoxicity are met ([Section 7.4](#))
- The investigator judges that continued administration of study drug would be detrimental to the patient's safety or well-being
- Protocol violation
- Lost to follow-up
- ALS progression
- Patient wants to enter another ALS trial or receive an experimental therapy for the treatment of ALS
- Death
- The Sponsor requests that the patient permanently discontinue study drug

7.2.1. Management of Patients after Permanent Discontinuation of Study Drug

If study drug is permanently discontinued, the patient should be encouraged to remain in the trial to continue to obtain outcome measures and safety data via a phone or video call.

There are several options for a patient after permanently discontinuing study drug:

- Patient agrees to continue to return to clinic for all remaining in-clinic study visits and agrees to all planned remote visits.

- Patient only agrees to complete the early discontinuation (ED) visit as soon as possible after the decision is made, the follow-up visit 4 weeks after the last dose taken, and additional follow-up visits dependent upon lab results; it is preferred these are done in clinic but can be done remotely if that is not feasible.
- Patient only agrees to complete the ED visit; it is preferred this is done in clinic but can be done remotely if that is not feasible.
- Patient only agrees to remote visits to obtain patient study data.
- Patient agrees to a mix of remote and in-clinic visits to obtain study data
- Patient only agrees to allowing contact for determination of vital status
- Patient withdraws consent (see [Section 7.6](#)) and does not agree to any further study procedures or visits.

Assessments obtained at the early discontinuation (same as FU Visit at Week 52) are listed in the Schedule of Activities. Details of the assessments to be performed at the additional visits following drug discontinuation, should the patient agree to be followed via either in-clinic or remote visits, can be found in the Study Manual.

Patients that have not withdrawn consent and have difficulty returning for all remaining study visits can be contacted by phone or video call to obtain patient study data.

7.3. Renal Function Monitoring and Study Drug Management

Reldesemtiv will be held if:

- Both $eGFR_{Cr}$ and $eGFR_{CysC} < 30.0$ ml/min/1.73m² or
- urine protein creatinine ratio (UPCR) is ≥ 3 mg protein/mg creatinine (or ≥ 339 mg protein/mmol creatinine)

Reldesemtiv may be restarted at half the dose, or 1 tablet twice a day (150 mg BID) when:

- Both $eGFR_{Cr}$ and $eGFR_{CysC}$ is > 40.0 ml/min/1.73m² and
- UPCR is ≤ 1.5 mg protein/mg creatinine (or ≤ 170 mg protein/mmol creatinine)

Serum cystatin C, $eGFR_{CysC}$, serum creatinine, and $eGFR_{Cr}$ will be obtained. These renal related laboratory results will be reviewed by the local investigator and the study drug should be held or restarted in the event the above criteria are met.

Abnormal renal function tests meeting the above criteria will be repeated. The site investigator and medical monitor should discuss and agree that study drug can be resumed or alternatively permanently discontinued. Agreement by the patient, site investigator, and medical monitor must occur for study drug to be resumed at a reduced dose.

1. If reldesemtiv is re-initiated, it must be at the lower dose of 150 mg BID,
or
2. If the abnormal renal function test requiring interruption of reldesemtiv occurred during administration of 150 mg twice daily, reldesemtiv 150 mg twice daily may be resumed once the laboratory value in question has returned to the threshold specified in the

protocol for re-initiation of reldesemtiv; however, should the same abnormal renal function test requiring reldesemtiv interruption recur, the patient must be permanently discontinued from reldesemtiv.

To accomplish this, the medical monitor may direct the laboratory assessments (serum cystatin C, eGFR_{CysC}, serum creatinine, eGFR_{Cr}, and UPCR) to be repeated as often as twice a week until a final disposition is reached (ie, re-initiation of study drug at 150 mg BID or permanent discontinuation) is reached.

Criteria for permanent discontinuation of study drug due to potential renal toxicity

Study drug **must** be discontinued permanently if the patient requires hemodialysis.

7.4. Liver Function Monitoring and Study Drug Management

ALT, AST, alkaline phosphatase (ALP) and total (and if available, direct) bilirubin will be obtained in accordance with the schedule of events.

Patients with abnormal hepatic laboratory values [ie, ALP, AST, ALT, total bilirubin (TBL)] or signs/symptoms of hepatitis as described below meet the criteria for permanent discontinuation of reldesemtiv. Patients who meet the criteria for permanent discontinuation must not be re-challenged.

Criteria for permanent discontinuation of reldesemtiv due to potential hepatotoxicity

- Elevation of either AST or ALT according to the following schedule:

Baseline AST or ALT Value	AST or ALT Elevation
Any	>8 × ULN at any time
Any	>5 × ULN but <8 × ULN for ≥2 weeks
Any	>5 × ULN but <8 × ULN and unable to adhere to enhanced monitoring schedule
Any	>3 × ULN with clinical signs or symptoms that are consistent with hepatitis (such as right upper quadrant pain/tenderness, fever, nausea, vomiting, jaundice)

OR

- TBL >3 × ULN at any time

If any of the criteria above are met, reldesemtiv must be permanently discontinued.

Study drug **must** be also discontinued permanently if ALL of the criteria below are met:

- TBL >2 × ULN or international normalized ratio (INR) >1.5

AND

- increased AST or ALT from the relevant baseline value as specified below:

Baseline AST or ALT Value	AST or ALT Elevation
<ULN	>3 × ULN

AND

- no other cause for the combination of the above laboratory abnormalities is apparent. Important alternative causes for elevated AST/ALT and TBL values include, but are not limited to:
 - hepatobiliary tract disease
 - viral hepatitis (eg, Hepatitis A/B/C/D/E, Epstein-Barr Virus, cytomegalovirus, Herpes Simplex Virus, Varicella, toxoplasmosis, and Parvovirus)
 - right sided heart failure, hypotension, or any cause of hypoxia to the liver causing ischemia
 - exposure to hepatotoxic agents/drugs or hepatotoxins, including herbal and dietary supplements, plants and mushrooms
 - heritable disorders causing impaired glucuronidation (eg, Gilbert’s Syndrome, Crigler-Najjar syndrome) and drugs that inhibit bilirubin glucuronidation (eg, indinavir, atazanavir)
 - alpha-one antitrypsin deficiency
 - alcoholic hepatitis
 - autoimmune hepatitis
 - Wilson’s disease and hemochromatosis
 - nonalcoholic fatty liver disease including steatohepatitis
 - nonhepatic causes (eg, rhabdomyolysis, hemolysis)

Patients who clearly meet the criteria for permanent discontinuation must never be re-challenged.

Additional Clinical Assessments and Observation

All patients in whom the study drug is permanently discontinued due to meeting the hepatic safety threshold as described above are to undergo a repeat test and a period of “close observation” until abnormalities have stabilized and returned to normal (or returned to the patient’s baseline levels). Assessments that are to be performed during this period include:

- Retesting of AST, ALT, ALP, total (and if available, direct) bilirubin, and obtaining an INR within 48 hours
- In cases of TBL >2 × ULN or INR >1.5, retesting of liver tests, total (and if available, direct) bilirubin, and INR within 48 hours

Confirmed abnormal liver function tests (LFTs) and INR should be repeated 2-3 times weekly then weekly or less if abnormalities stabilize or the study drug has been discontinued and the patient is asymptomatic. Follow the patient and the laboratory tests (ALT, AST, TBL, INR) until all laboratory abnormalities return to baseline or normal.

- Initiate investigation of alternative causes for elevated AST or ALT and/or elevated TBL, as warranted:
 - Obtain complete blood count (CBC) with differential to assess for eosinophilia
 - Obtain serum total immunoglobulin IgG, Anti-nuclear antibody (ANA), Anti Smooth Muscle Antibody, and Liver Kidney Microsomal antibody 1 (LKM1) to assess for autoimmune hepatitis
 - Obtain serum acetaminophen (paracetamol) levels
 - Obtain viral serologies
 - Obtain creatine phosphokinase, haptoglobin, lactate dehydrogenase, and peripheral blood smear
 - Perform appropriate liver imaging if clinically indicated
- Obtain a more detailed history of:
 - Prior and/or concurrent diseases or illness
 - Exposure to environmental and/or industrial chemical agents
 - Symptoms (if applicable) including right upper quadrant pain, hypersensitivity type reactions, fatigue, nausea, vomiting and fever
 - Prior and/or concurrent use of alcohol, recreational drugs and special diets
 - Concomitant use of medications (including non-prescription medicines and herbal and dietary supplements), plants, and mushrooms
- Obtain hepatology consult, as warranted (liver biopsy may be considered in consultation with an hepatologist)

Clinically significant elevated transaminases and/or bilirubin and manifestations of liver toxicity (eg, rash, abdominal pain, nausea and vomiting, fatigue, dark-colored urine, light-colored bowel movements, jaundice, loss of appetite, fever) including elevations that prompt study drug discontinuation are considered adverse events of special interest and must be recorded on the appropriate CRF and reported to Cytokinetics Drug Safety within 24 hours of awareness.

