7.1. Temporary Study Drug Interruption

Initially, any study drug interruption should be considered temporary unless permanent study drug discontinuation is mandated by the protocol.

A temporary study drug interruption:

- Will be implemented when a predefined safety threshold has been met (see [Section 7.3](#) for Renal Function Monitoring).
- May be considered by the investigator in the case of an AE/SAE or for another reason.

If a temporary study drug interruption occurred because a safety threshold was met, treatment may be resumed at a lower dose as outlined in [Section 7.3](#) (Renal Function Monitoring).

Patients who experience a laboratory abnormality or adverse event requiring interruption of reldesemtiv while receiving 150 mg twice daily may resume reldesemtiv 150 mg twice daily once the laboratory value in question has returned to the threshold specified in the protocol for re-initiation of reldesemtiv; however, should the same laboratory abnormality requiring interruption of reldesemtiv recur, the patient must be permanently discontinued from reldesemtiv.

If the study drug was temporarily interrupted because of an AE/SAE that was not felt to be related to study drug, the investigator should make the best effort to resume study drug as soon as practically possible, assuming there are no remaining safety concerns.

If dosing is interrupted for more than 7 consecutive days, based upon clinical judgement, the investigator may choose to see the patient in clinic or via a phone or video call prior to study drug resumption.

All temporary study drug interruptions (stop and start dates and times and reason for interruption) should be recorded in the CRF and the Medical Monitor should be notified.

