8.3.1.3. Definition of Adverse Event of Special Interest

Adverse events of special interest (AESI) in the CY 5032 study are defined based on clinical and laboratory parameters.

Clinically significant elevated transaminases and/or (total and if available, direct) bilirubin and manifestations of liver toxicity (e.g., rash, abdominal pain, nausea and vomiting, fatigue, dark-colored urine, light-colored bowel movements, jaundice, loss of appetite, fever) including elevations that prompt study drug discontinuation, are considered adverse events of special interest and should be reported to Cytokinetics Drug Safety within 24 hours of awareness on an AESI Report Form.

Any of the following criteria should be reported as Liver-Related AESIs:

- Manifestations of liver toxicity
- ALT or AST $>8 \times$ ULN
- ALT or AST $>5 \times$ ULN but $<8 \times$ ULN for ≥ 2 weeks;
- ALT or AST $>5 \times$ ULN but $<8 \times$ ULN and unable to adhere to monitoring;
- ALT or AST $>3 \times$ ULN w/signs or symptoms consistent with hepatitis (ie, right upper quadrant pain /tenderness, fever, nausea, vomiting, jaundice)
- TBL $>3 \times$ ULN
- TBL $>2 \times$ ULN or INR >1.5 AND ALT or AST $>3 \times$ ULN AND no alternative cause is apparent

Manifestations of renal toxicity, including clinically significant decreases in $eGFR_{Cr}$ and $eGFR_{CysC}$ and increases of UPCr, are also considered adverse events of special interest and should be recorded on the appropriate CRF and reported to Cytokinetics Drug Safety within 24 hours of awareness on an AESI Report Form.

Any of the following criteria should be reported as Renal-Related AESIs:

- Manifestations of renal toxicity
- Both $eGFR_{Cr}$, $eGFR_{CysC} < 30.0$ ml/min/1.73m²
- $UPCr \geq 3$ mg protein/g creatinine (or ≥ 339 mg protein/mmol creatinine)

In addition, if reldsemtiv has been temporarily interrupted or permanently discontinued related to renal labs that don't meet the above criteria, this is also considered as Renal-Related AESIs.

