8.2.2. Summaries of Adverse Events of Special Interest

Adverse events of special interest (AESI) in the CY 5032 study are defined based on clinical and laboratory parameters. Results for AESI will be reviewed individually. No summary table will be provided.

Clinically significant elevated transaminases and/or (total and if available, direct) bilirubin and manifestations of liver toxicity (e.g., rash, abdominal pain, nausea and vomiting, fatigue, dark-colored urine, light-colored bowel movements, jaundice, loss of appetite, fever) including elevations that prompt study drug discontinuation are considered adverse events of special interest and should be reported to Cytokinetics Drug Safety within 24 hours of awareness on an AESI Report Form.

Any of the following criteria should be reported as Liver-Related AESIs:

- Manifestations of liver toxicity
- ALT or AST $>8 \times$ ULN
- ALT or AST $>5 \times$ ULN but $<8 \times$ ULN for ≥ 2 weeks
- ALT or AST $> 5 \times$ ULN but $<8 \times$ ULN and unable to adhere to monitoring
- ALT or AST $>3 \times$ ULN w/signs or symptoms consistent with hepatitis (i.e., right upper quadrant pain /tenderness, fever, nausea, vomiting, jaundice)
- TBL $>3 \times$ ULN
- TBL $>2 \times$ ULN or INR >1.5 AND ALT or AST $>3 \times$ ULN AND no alternative cause is apparent

Manifestations of renal toxicity, including clinically significant decreases in $eGFR_{Cr}$ and $eGFR_{CysC}$ and increases of UPCr, are also considered adverse events of special interest and should be recorded on the appropriate CRF and reported to Cytokinetics Drug Safety within 24 hours of awareness on an AESI Report Form.

Any of the following criteria should be reported as Renal-Related AESIs:

- Manifestations of renal toxicity
- Both $eGFR_{Cr}$, $eGFR_{CysC} < 30.0$ ml/min/1.73m²

- UPCR \geq 3 mg protein/g creatinine (or \geq 339 mg protein/mmol creatinine)

In addition, if reldsemtiv has been temporarily interrupted or permanently discontinued related to renal labs that don't meet the above criteria, this is also considered as Renal-Related AESIs. Study drug dose management with the potential for a dosing interruption and down-titration of dose will be applied.

8.3. Total Duration of Therapy, Average Daily Dose, Maximum Daily Dose, Final Daily Dose of Study Medication, and Compliance

Total duration of treatment and exposure of study drug per day will be summarized overall.

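### Protocol 7.4: an AST or ALT of exactly 8 × ULN meets no transaminase-only stopping row, although values just below and just above it can require a stop (minor wording error)

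*Protocol*

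**What the plan says.** Protocol 7.4 lists the AST/ALT elevations that force permanent discontinuation, with no re-challenge. Three rows start above 5 × ULN and depend on no symptom or other laboratory value:

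- ">8 × ULN at any time"
- ">5 × ULN but <8 × ULN for ≥2 weeks"
- ">5 × ULN but <8 × ULN and unable to adhere to enhanced monitoring schedule"

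The other hepatic stops in 7.4 need something more. One is AST or ALT >3 × ULN with signs or symptoms of hepatitis. Another is total bilirubin (TBL) >3 × ULN. The third is a combined rule: TBL >2 × ULN or INR >1.5, with AST or ALT >3 × ULN and no other apparent cause. The only baseline row listed for the combined rule is <ULN.

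The liver AESI bullets in Protocol 8.3.1.3 and SAP 8.2.2 use the same strict bounds at 8. Protocol 8.3.1.3 opens, however, with a general definition that has no numeric limit: "Clinically significant elevated transaminases and/or (total and if available, direct) bilirubin". SAP 8.5 tabulates ALT/AST in adjoining categories, >5x to 8x ULN and >8x ULN.

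**The concern.** A stopping rule should not become more lenient as the value gets worse. Here the upper row begins strictly above 8 and the two middle rows end strictly below it, so the boundary value belongs to no row. Nothing in the protocol suggests that 8 × ULN was meant to be exempt.

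The rule matters because Protocol 2.3.1.1 names the 7.4 criteria as part of the hepatic mitigation strategy, after hepatic findings in CY 5022. The follow-up package in 7.4 (repeat tests and INR within 48 hours, close observation) is written for patients stopped for meeting a hepatic threshold, so a value that meets no criterion does not trigger it. There is no mandatory hepatic hold behind it either: the threshold-based interruption in Protocol 7.1 points to the renal rules in 7.3.

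**Working it through.** The plan gives no figure to reproduce. The check applies the inequalities as written.

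**Inputs.** From Protocol 7.4, with x = AST or ALT divided by ULN:

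- Row A: x > 8, at any time.
- Row B: 5 < x < 8, for at least 2 weeks. This is read literally: the value must be in the band at the reading that completes the two weeks.
- Row C: 5 < x < 8, and the patient cannot follow enhanced monitoring.

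No hepatitis symptoms and normal TBL and INR are assumed, so the other rules are silent. The documents give no ULN; 35, 40 and 50 U/L are assumed, with whole-number results.

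**At x = 8.** Row A asks whether 8 > 8: no. Rows B and C ask whether 8 < 8: no. No row applies.

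**At ULN 40.** 319/40 = 7.975, 320/40 = 8.000, 321/40 = 8.025.

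| Situation | 319 U/L | 320 U/L | 321 U/L |
|---|---|---|---|
| Cannot follow enhanced monitoring, one reading | stop (C) | no criterion | stop (A) |
| Same value throughout ≥2 weeks | stop (B) | no criterion | stop (A) |
| 280 U/L (7.000×) first, then this value completing two weeks | stop (B) | no criterion | stop (A) |
| Adherent patient, one reading | no stop | no stop | stop (A) |

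The first three lines show the reversal. The last does not: for an adherent patient with one reading, 8 × ULN is treated like any other value between 5 and 8.

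**Other ULNs, row C, one reading.**

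- ULN 35: 279 (7.971×) stop, 280 (8.000×) no criterion, 281 (8.029×) stop.
- ULN 50: 399 (7.980×) stop, 400 (8.000×) no criterion, 401 (8.020×) stop.

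**After the edit.** With 5 < x ≤ 8 in rows B and C, the 320 column becomes stop, stop, stop, no stop; the other columns do not change. With x ≥ 8 in row A instead, the 320 column becomes stop in all four lines.

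**The case against.** The strongest case against the point is that it has no practical consequence. It takes a result at exactly 8.000 × ULN, together with either inability to follow enhanced monitoring or a two-week elevation, no symptoms, no qualifying bilirubin or INR finding, and an investigator who does nothing. Protocol 7.1 allows interruption: "May be considered by the investigator in the case of an AE/SAE or for another reason". Protocol 7.2 gives, as a reason to stop, "The investigator judges that continued administration of study drug would be detrimental". Protocol 8 says that immediate safety concerns should go to the Medical Monitor. The study was also terminated early (SAP 4.2).

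Most of this stands, and it limits the size of the point. It does not remove it, because these routes are discretionary or need further findings, whereas the 7.4 rows are mandatory.

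A reader might go further and infer one of the following. The documents support none of them.

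- *Patients at 8 × ULN would be left on drug.* The protocol gives the investigator ample grounds to hold or stop, and a clinician would very probably act.
- *The event would go unreported as an AESI.* The general definition quoted above has no gap at 8, and Protocol 7.4 makes reporting of such elevations mandatory within 24 hours. It depends on a judgement of clinical significance, but it largely captures the value.
- *The safety tables would be wrong.* SAP 8.2.2 says "Results for AESI will be reviewed individually. No summary table will be provided", and the SAP 8.5 categories, as normally read, place 8 × ULN in the >5x to 8x row.

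**Conclusion.** The wording of Protocol 7.4 is wrong at one value, and the point is minor. Exactly 8 × ULN meets no transaminase-only mandatory stop, while values on either side do if the patient cannot follow enhanced monitoring or if the reading completes two weeks of elevation.

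The affected value is 280, 320 or 400 U/L at an assumed ULN of 35, 40 or 50. No percentage or number of patients can be derived from the documents, and with the study terminated few or none would be affected. No estimate, error rate or planned table changes. The conclusion rests on the literal inequalities, which agree across Protocol 7.4, Protocol 8.3.1.3 and SAP 8.2.2. The U/L figures rest on the assumed ULNs.

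**What to change.** In the two middle-band rows of Protocol 7.4, change <8 × ULN to ≤8 × ULN. This agrees with the SAP 8.5 categories as normally read. Changing the top row to ≥8 × ULN would also close the gap and is more conservative, because a single reading at 8 × ULN would then stop an adherent patient too. It would, however, put the boundary value on the other side from SAP 8.5.

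Make the same edit in the two matching bullets of Protocol 8.3.1.3 and the two in SAP 8.2.2, all at the same time. Revising the SAP alone would create a mismatch with the protocol where the two now agree.

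The cost is six one-symbol edits (2 + 2 + 2), four of them in the protocol, with no new test, visit or analysis. Protocol 10.1.1 requires IRB/IEC approval of amendments before implementation, and about 85 sites were planned. A separate amendment for this alone is not worthwhile in a terminated study; bundle the edits with any other amendment. At the least, correct the wording before it is reused in another protocol.

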8.3.1.9. Follow-up of AEs and SAEs

The investigator is obligated to perform or arrange for the conduct of supplemental measurements and/or evaluations as medically indicated or as requested by Cytokinetics to elucidate the nature and/or causality of the AE or SAE as fully as possible. This may include additional laboratory tests or investigations, histopathological examinations, or consultation with other health care professionals.

If a patient dies during participation in the trial or during a recognized follow-up period, the investigator is encouraged to provide Cytokinetics with a copy of any post-mortem findings including histopathology if it has been performed.

Non-serious adverse events must be followed until they resolve or until the patient completes the trial, whichever comes first. Serious adverse events and adverse events of special interest still ongoing at the end of study must be followed up until resolution or stabilization, or until the event outcome is provided, eg, death. Reporting may continue after the follow-up visit and database lock.

New SAEs occurring after the 4-week follow-up period must be reported to the Cytokinetics Drug Safety department within 24 hours of the investigator's knowledge of the event, only if considered by the investigator to be causally related to previous exposure to the study drug.

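### INR >1.5 is one limb of a mandatory hepatic stopping rule, but no scheduled panel includes INR and the only explicit order for a first INR comes after the drug has been stopped

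*Protocol*

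**What the plan says.** Protocol Section 7.4 sets several hepatic criteria for permanent discontinuation. One is a combined rule with three conditions, all of which must hold:

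- "TBL >2 × ULN or international normalized ratio (INR) >1.5";
- AST or ALT above 3 × ULN in a patient whose baseline was below ULN;
- no other apparent cause for the combination.

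If all three are met, stopping is mandatory. Section 8.3.1.3 uses a similar combination, without the baseline restriction, as a liver-related adverse event of special interest (AESI). SAP Section 8.2.2 repeats that definition.

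On routine monitoring, 7.4 says: "ALT, AST, alkaline phosphatase (ALP) and total (and if available, direct) bilirubin will be obtained in accordance with the schedule of events". INR is not named there.

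INR is first ordered under the 7.4 subheading on additional clinical assessments: "Retesting of AST, ALT, ALP, total (and if available, direct) bilirubin, and obtaining an INR within 48 hours". The lead-in to that list restricts it to "All patients in whom the study drug is permanently discontinued due to meeting the hepatic safety threshold as described above".

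A later sentence in the same place reads: "Follow the patient and the laboratory tests (ALT, AST, TBL, INR) until all laboratory abnormalities return to baseline or normal". The sentence before it lets testing become less frequent "if abnormalities stabilize or the study drug has been discontinued and the patient is asymptomatic".

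**The concern.** A mandatory stopping rule should be evaluated in the same way in every patient who reaches its enzyme threshold. Here one of the two alternative laboratory inputs is not collected on schedule, and the only explicit order for a first measurement comes after the decision it is meant to inform. Two sites could have patients with identical scheduled results and differ in whether INR is measured, and so in whether drug is stopped.

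Section 2.3.1.1 relies on liver monitoring and the 7.4 discontinuation criteria as the hepatic mitigation, citing findings in CY 5022, so those criteria should be fully assessable. The INR-based AESI criterion has the same weakness.

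The renal rule in Section 7.3 makes a useful contrast. Its hold criteria use eGFR from creatinine, eGFR from cystatin C and UPCR. All three are on the scheduled panel, and the medical monitor may direct repeats of those named tests.

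**Working it through.** No sample-size or error-rate figure is involved. The check is a count of visits and a reading of the sections side by side.

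**Is INR on any scheduled panel?** Liver tests appear in the Schedule of Activities (Protocol 1.3) at Day 1 and Weeks 6, 12, 18, 24, 36, 48 and 52.

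- All liver-test visits: 8.
- Less Day 1 (baseline) and Week 52 (no dosing): 8 − 2 = 6 post-baseline on-treatment visits.
- Less Week 48, the last day of dosing (Section 6.4): 6 − 1 = 5 visits that precede further dosing in this study.
- Visits with INR, from footnote 3 (quarterly panel), footnote 4 (Weeks 6 and 18) and Table 6: 0 of 6, and 0 of 5.

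The SAP copy of the schedule (Table 1) matches. Apart from the abbreviation list, INR appears in the protocol only in 7.4 and 8.3.1.3, and in the SAP only in 8.2.2. SAP 8.5 summarizes ALT, AST, ALP and bilirubin, not INR.

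**Where would INR alone decide?** Going through the 7.4 criteria for a patient on drug:

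| State on drug | Mandatory stop without INR? |
|---|---|
| AST/ALT >8 × ULN | Yes |
| AST/ALT 5–8 × ULN for at least 2 weeks, or enhanced monitoring not possible | Yes |
| AST/ALT >3 × ULN with hepatitis signs or symptoms | Yes |
| TBL >3 × ULN | Yes |
| AST/ALT >3 × ULN, baseline <ULN, TBL >2 × ULN, no other cause | Yes, through the bilirubin limb |
| AST/ALT >3 to 5 × ULN, baseline <ULN, TBL ≤2 × ULN, no symptoms, no other cause | No: INR decides |
| As the row above, but 5–8 × ULN for under 2 weeks with enhanced monitoring followed | No: INR decides |

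**How could an INR arise in the last two rows?**

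1. *General provisions.* Unscheduled samples and additional tests are permitted (Section 8, Appendix 2), and immediate safety concerns go to the Medical Monitor (Section 8). Once the rise is an adverse event, 8.3.1.9 makes the investigator "obligated to perform or arrange for the conduct of supplemental measurements and/or evaluations as medically indicated or as requested by Cytokinetics". These routes rest on judgement or on a request.
2. *The 7.4 follow-up sentence that names INR.* Its scope is unclear. It sits in the post-discontinuation text, but the preceding taper wording treats discontinuation as one alternative, which suggests that some covered patients are still on drug. On either reading it sets no first INR at >3 × ULN.
3. *Enhanced monitoring.* This appears only in the 5–8 × ULN row, as "unable to adhere to enhanced monitoring schedule". Its content is not given, and it does not reach 3–5 × ULN.

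None of the three ties a first INR to AST/ALT >3 × ULN on drug. From Week 24 the scheduled liver tests are 12 weeks apart (Weeks 24, 36, 48), so the next scheduled visit is not a prompt substitute.

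**The case against.** The strongest reply is that the combined rule is a triggered clinical evaluation and was never meant to be read off scheduled labs. Its no-other-cause condition needs a work-up that is on no routine panel either, so leaving a confirmatory test unscheduled is a legitimate choice. Safeguards also exist without INR:

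- The investigator reviews every laboratory report (8.2.4).
- A clinically significant transaminase rise is an AESI reportable within 24 hours whatever the INR (7.4, 8.3.1.3), and 8.3.1.9 then imposes a duty, not mere permission.
- Drug can be interrupted or stopped on judgement under 7.1 and 7.2.
- SAP 8.5 tabulates the >3 to 5 × ULN category.

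Entrants had already tolerated reldesemtiv for at least 24 weeks (2.3.1), and the CY 5022 hepatic findings were most frequent at 450 mg twice daily, a dose not used here (2.3.1.1). The laboratory manual, the Study Manual and the enhanced monitoring schedule were not available for this review and could contain a reflex INR.

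Most of this stands as a limit on size. The enzyme signal is seen, and a careful investigator may well order an INR. But seeing the rise does not evaluate the INR limb, and the 8.3.1.9 duty still turns on medical indication or a sponsor request. If a manual does specify the test, the protocol should point to it.

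It is also fair that 0 of 6 counts routine panels, and a conditional test would not change that count. The count shows only that the schedule does not supply the input.

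A further objection is that a trigger at >3 × ULN in everyone is wider than a rule limited to baseline below ULN. This fails because the AESI criterion uses INR >1.5 with AST/ALT >3 × ULN and no baseline restriction.

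**Conclusion.** The concern holds. The protocol can be followed exactly and still leave the INR limb unevaluated in an on-drug patient who has reached the enzyme threshold. That is confirmed by the text. Uneven application is a possible consequence and has not been shown to occur.

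The affected group is narrow: baseline below ULN, AST/ALT >3 × ULN, TBL ≤2 × ULN, no hepatitis symptoms, no stand-alone criterion met and no other apparent cause, mainly at 3–5 × ULN. The documents give no rate of AST/ALT >3 × ULN, so the number of patients cannot be estimated. Because the study was stopped early (SAP Sections 1, 4.2 and 9), the practical effect in this trial is small. The conclusion assumes that the unavailable manuals do not already require the test. This should be corrected, but it does not undermine the trial's safety analysis.

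**What to change.** In Section 7.4, require an INR together with repeat AST, ALT, ALP and bilirubin within 48 hours whenever AST or ALT exceeds 3 × ULN on drug. List INR as a conditional test in Table 6 and in Schedule of Activities footnotes 3 and 4, and make the same edit to those two footnotes in SAP Table 1. Keep the post-discontinuation INR, the stopping thresholds and the AESI definition as they are.

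The cost is protocol wording and an occasional unscheduled blood draw in few patients, repeated if an elevation recurs. Some draws will be in patients whose baseline was not below ULN; there the result informs the AESI criterion but not the combined stopping rule. The home health vendor is provided for Weeks 6 and 18 only, so its use for the reflex draw would have to be added, or the draw done in clinic. No SAP analysis changes, since SAP 8.5 does not use INR.
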